1. **Unconsented data:** SIHHC (hospital discharge projects) taking part in the study (Sites 1-2, 7-13 using clinically led services; Sites 3-4, 14-20 using non-clinically led services) will be asked to provide identifying and demographic data (forename, surname, aliases, date of birth, sex, current or previous postcodes, nationality, ethnicity, NHS number) for service users during the period November 2013 to a maximum of November 2016. However, note that for some services we will collect data that ends before 2016 as some will have been shut down before this time period and in some we may collect data at an earlier point, providing we receive the appropriate permissions and ethical and CAG approvals.
2. **Consented data from a subset of study fieldwork sites (n=6 sites):** We will collect data on 252 individuals across 4 sites with SIHHC (hospital discharge) schemes (two sites that are clinically led (Sites 1&2), two sites that are non-clinically led (Sites 3&4)) and on 126 individuals across two sites with standard /usual care (Sites 5&6), giving 378 individuals in total (63 per site x 6 sites). The data collection for this part of the work is contained in a baseline, exit and 3-month follow up data questionnaire and will collect information on demographic information, along with dates of contact with SIHHC services, past use of health and social care services, mental health services, smoking, alcohol, and drug taking history, prison and homeless history, employment, user satisfaction with service delivery, and data on quality of life (EQ5D). The voluntary sector hospital discharge projects will be asked to help collect this data on behalf of the research team as part of their routine outcomes monitoring and will be reimbursed for doing so at a rate of £20 per completion. The data flow chart shows how this work will be integrated with WP1 for practical purposes.
3. The data flow chart shows how this work will be integrated with WP1 for practical purposes.

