We will provide data from the 20 sites and Find and Treat to the Health & Social Care Information Centre (HSCIC). These records will be list cleaned and then linked by HSCIC to the Hospital Episode Statistics (HES) database to provide data on hospitalisations and A&E attendances and deaths for individuals in the 20 sites and Find and Treat database. In order to be able to identify co-morbidities more accurately we will request data on all previous admissions for these groups for identification of

comorbidities but analyses of admission rates will be confined to the period November 2008 – November 2016.

Study design:

We will construct a virtual cohort that will take first date of admission as the entry point (earliest November 2008) or, for control groups an admission matched by month and year restricted to individuals over the age of 18. Exit from the virtual cohort will be at the end of November 2016 or, if earlier, date of death. We will conduct person-level analyses using Poisson regression to compare overall hospitalisation rates, emergency admission rates, all cause mortality and avoidable mortality rates in:

- 1) Homeless people using the different categories of SIHCC service (clinically led services - sites 1&2, 7-13; non-clinically led services - sites 3&4, 14-20)
- 2) Find and Treat Homeless population and sites 5&6 with standard usual care
- 3) Socially deprived non-homeless population.

We will also conduct analyses at the level of the hospital admission whereby through knowledge of the dates of SIHCC involvement and service user group we will be able to classify hospital admissions in the period November 2008- November 2016) into the following groups:

- 1) Admissions in a socially deprived non homeless population
- 2) Admissions in the general homeless population (Find and Treat data)
- 3) Admissions in homeless service users prior to their first engagement with SIHCC
- 4) Admissions in homeless service users where there is evidence of SIHCC support for that admission
- 5) Admissions in homeless service users that occur following SIHCC support but where there is no record of support for the subsequent admission.

We will use Cox regression survival models and Kaplan Meir plots (accounting for clustering at the level of the hospital and individual) to explore how admissions in these groups compare in terms of the following primary outcomes:

- 1) Time from discharge to next A&E attendance

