- 2) 28 day emergency readmission rates (these are a commonly used indicator within the NHS)
- 3) Time from discharge to next hospital inpatient readmission

Secondary outcomes we will examine include:

- 1) Time from admission to death
- 2) Duration of inpatient admission
- 3) Time from admission to mortality from causes amenable to healthcare
- 4) Time from discharge to admission with ambulatory care sensitive (ACS) conditions
- 5) Time from discharge to next planned admission,
- 6) Overall readmission rates
- 7) Unscheduled readmission rates
- 8) All cause mortality
- 9) International Classification of Diseases 10th Revision chapter-specific mortality
- 10) In-patient costs using Health Resource Group

For those service users with quality of life data we will explore how this changes following involvement of services and how it compares to the measures of quality of life derived from studies within Find and Treat service users and within socially deprived non-homeless groups.

A variety of mortality groupings have been developed to identify causes of death that could be considered avoidable through better medical care depending on age at which they occur. The proposals for the Public Health Outcome Monitoring framework take a similar approach and focus on key areas of avoidable mortality namely: mortality from suicide, communicable diseases, excess

seasonal mortality and, in persons aged less than 75 years, cardiovascular disease, cancer, chronic liver disease and chronic respiratory diseases. All of these are useful indicators within homeless populations.

Sample size:

Our sample size is based upon our estimates of historical data from the two types of SIHHC services (non-clinically led SIHHC services vs. clinically led SIHHC). We estimate that each type will have data from approximately 2,208 individuals for the two-year duration of the study, based on the services seeing on average 92 people per month.

From previous health service evaluation data on homeless groups we expect hospitalisation rates to be 0.7 episodes per person-year for homeless individuals admitted to hospital. An important reduction in readmission rates would be 10%. To undertake a sample size calculation to determine the study size required to detect such a reduction in readmission rates, the following variables were defined:

μ_0 = mean readmission rate in the baseline group = 0.7 episodes per person-year

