Confounding variables: As this is a virtual cohort, we will not be able to collect a complete set of confounding variable data on individuals at entry to the study. Where data is provided by SIHHC services we will include age (year and month only), sex. As a result of the lack of baseline data will use historical HES data to determine past medical history from the age of 18 which will be used to create a variable to control for co-morbid conditions and historical hospital usage. Analyses will therefore control for age, gender, comorbidities (identified from HES data) and reason for admission, classified by Healthcare Resource Group (HRGs – groupings of treatment episodes which are similar in resource use and clinical response). Subgroup analyses will compare the different types of SIHCC services. Where provided by the SIHHC services, we will also control in subgroup analysis for medical symptoms, past use of health and social care services, mental health services, smoking, alcohol, and drug taking history, prison and homeless history, employment history.

Health Economics Analysis:

This analysis will cover three economic models. The primary analysis will be a cost effectiveness model (linked to effectiveness data described in the comparative effectiveness section). This model will take an NHS perspective, with costs based on the linked HES data analysis and outcomes based on morbidity and mortality data. Outcomes of homeless users of the two types of SIHHC service (clinically led and non-clinically led) will be compared to each other and homeless controls. Outcomes used for this analysis will include: 1. Overall hospital readmission rates; 2. Unscheduled readmission rates; 3. 28-day emergency readmission rates. Cost estimates will be calculated using national NHS

tariff data, and will include length of hospital stay, emergency admissions, and fixed and variable costs estimates for each of the SIHHC services.

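### Admissions before first SIHHC engagement (group 3) are selected on a later engagement, so using them as a reference for supported admissions (group 4) biases time to inpatient readmission in favour of SIHHC

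*Protocol*

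**What the plan says.** Under Data sets used for WP2, the hospital discharge projects supply identifying data "for service users during the period November 2013 to a maximum of November 2016". Under Comparative Effectiveness Analysis, Study design, the protocol then states that "through knowledge of the dates of SIHCC involvement and service user group we will be able to classify hospital admissions" into five groups, over November 2008 to November 2016. Three of the groups concern scheme users:

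- group 3: "Admissions in homeless service users prior to their first engagement with SIHCC";
- group 4: "Admissions in homeless service users where there is evidence of SIHCC support for that admission";
- group 5: later admissions of the same people with no record of support.

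Group 1 is a deprived non-homeless population and group 2 is the Find and Treat population.

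Cox models and Kaplan-Meier plots, allowing for clustering by hospital and individual, are to be used "to explore how admissions in these groups compare in terms of the following primary outcomes". The outcomes are time to next A&E attendance, 28-day emergency readmission and "Time from discharge to next hospital inpatient readmission". Time from admission to death is a secondary outcome. No reference group is named and no contrast is excluded.

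Under Confounding variables: "Analyses will therefore control for age, gender, comorbidities (identified from HES data) and reason for admission". The same paragraph plans a variable built from HES history since age 18 that covers comorbidity and earlier hospital use. In the Study design text, matching by month and year is stated for control groups only.

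**The concern.** Group 3 is assigned with hindsight. A 2010 admission belongs to it only because the same person was alive and engaged with a discharge scheme in or after late 2013. People who died first, or who never came back, supply no group 3 admissions. If first engagement takes place at an inpatient admission that links to HES, every group 3 admission has an observed inpatient readmission and no death before it. Group 4 admissions have no guaranteed later event.

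The comparison of 4 with 3 is the natural before-and-after reading of the five groups, and nothing in the protocol warns against it. Membership of group 3 depends partly on the outcome, so an ineffective scheme would appear to delay readmission. For death the distortion runs the other way, because group 3 cannot include anyone who died before engaging. The stated covariates look backwards from the admission and cannot fully undo selection on a later event. Allowing for clustering changes standard errors, not bias.

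**Working it through.** **The plan's own figures.** Sample size: (0.84 + 1.96)² × (0.7 + 0.6) / (0.7 − 0.6)² = 7.84 × 1.3 / 0.01 = 1019 person-years per group, as stated. It does not depend on this point. The section supplies the yardstick: 0.6/0.7 = 0.857, and the stated 10% reduction gives 0.90.

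**Inputs from the protocol.** Admission rate 0.7 per person-year; an eight-year window, with support possible only in the last three years; censoring at November 2016 or death.

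**Inputs assumed, because the protocol gives none.** Probability that an admission is supported; variation in admission rates between people; mortality. Admissions are treated as instantaneous, and each engagement is at a linked inpatient admission.

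**Null simulation, unadjusted.** 20,000 people per scenario; Poisson admissions; support has no effect. Cox hazard ratio for time to inpatient readmission, group 4 v group 3 (annual death rate 0 / 0.04):

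| Rates between people | support 0.3 | support 0.6 | support 1.0 |
|---|---|---|---|
| equal | 0.85 / 0.88 | 0.90 / 0.91 | 0.96 / 0.96 |
| gamma, shape 2 | 0.75 / 0.74 | 0.83 / 0.83 | 0.91 / 0.89 |
| gamma, shape 0.7 | 0.72 / 0.74 | 0.82 / 0.81 | 0.88 / 0.87 |

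Readmission was observed for 100% of group 3 admissions and 57–70% of group 4. The equal-rates row isolates conditioning on the future. The lower rows add a second effect: frequent attenders contribute more admissions to group 3.

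**With the planned adjustment.** A separate null run used 2% annual mortality, frailty variance 0 to 2 and support probability 0.3 to 1.0. The hazard ratio was about 0.72–0.94 unadjusted and 0.84–0.98 after adjusting for prior admission rate, as a stand-in for the planned historical-use variable. Where rates are equal, prior use carries no information and adjustment cannot help.

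**28-day readmission (unadjusted), group 3 v group 4.** From 5.3% v 5.3% (equal rates, all admissions supported, no deaths) to 14.9% v 11.2% (shape 0.7, support 0.3, no deaths), a difference of 3.7 percentage points.

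**Is calendar restriction enough?** No. With admissions after November 2013 only, the unadjusted null hazard ratio falls further, to 0.47–0.68.

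**Confirming the cause.** When the comparator is all not-yet-engaged admissions, whatever happens later, the whole-period null hazard ratio returns to 0.99–1.05. Restricted to concurrent admissions it is 0.98–1.02 with equal rates and 1.09–1.34 with unequal rates. That residual is case mix and runs against SIHHC.

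**The case against.** **Certainty.** A reader might infer that the outcome is guaranteed in group 3 for all three primary outcomes. The protocol does not support that. A guarantee exists only for inpatient readmission, and only where first engagement is at a linked admission. The background section describes Pathway teams supporting A&E staff, so engagement may happen without an admission, and NHS numbers will be added only where possible, so some admissions will not link. HES covers planned as well as emergency admissions, so a later A&E attendance need not follow. 28-day readmission is not certain in either group.

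**Adjustment.** It is also tempting to quote the unadjusted hazard ratios as the size of the fault. That ignores the planned control for earlier hospital use, which removes much of the frequent-attender component. A residual in the same direction remains.

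**Status of the contrast.** The protocol does not single out 4 v 3. The sample size rests on clinically led versus non-clinically led services, and the primary economic analysis compares those with each other and with homeless controls. A reader should not conclude that the whole primary analysis fails. Comparison with group 1 is free of this fault. Comparison with group 2 avoids it only for admissions after screening, because an earlier admission of someone found by screening also required survival to that screening.

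**Calendar period.** Its absence from the covariate list could be settled in a statistical analysis plan, so it is not a separate fault here.

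These objections limit the scope and size. They do not make 4 v 3 a valid effect estimate, and the protocol leaves it open as one.

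**Conclusion.** The concern holds for one planned contrast. Group 3 is conditioned on later survival and engagement, so group 4 v group 3 is biased in favour of SIHHC for time to inpatient readmission. It is biased against SIHHC for time to death, although the size of that bias was not computed. With no true effect, the readmission hazard ratio after the planned type of adjustment is about 0.84–0.98. This reaches the 0.86–0.90 target when support is infrequent and admission rates are similar between people, and is smaller elsewhere. Any 28-day bias is at most about 4 percentage points in the unadjusted scenarios run and may be nil. A&E return was not computed; it should be biased the same way where the engaging admission came through A&E. The direction for readmission follows from the group definitions. The size rests on assumed support probability, heterogeneity and mortality, and on engagement at linked admissions.

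**What to change.** In Comparative Effectiveness Analysis, Study design, state that group 3 is reported descriptively. It should not be a reference group for effect estimates on time to readmission, A&E attendance, 28-day readmission or mortality.

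Base effect estimates on comparators whose eligibility is fixed by the time of their own discharge:

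- Find and Treat admissions counted only from the screening date onward, matched by month and year;
- admissions at the usual-care sites 5 and 6, where their data are available.

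Include calendar period and prior hospital use in these models.

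Two points need settling when this is written. Sites 5 and 6 belong to none of the five admission groups. They are also absent from the list of sites supplying unconsented data under Data sets used for WP2, although Appendix One, Box 1 ticks them for it; otherwise only 126 consented individuals are available there.

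Costs: the within-person before-and-after contrast is lost as evidence of effect, and Find and Treat admissions before screening are dropped. Residual case-mix differences, and the contrast between a London comparator and schemes across England, must be acknowledged as limitations.

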For homeless people, length of stay in hospital is reported to be three times longer than for other service users ([name], Halligan and Boyce, 2012). However, this is often attributed to the complexity of homeless people's presenting health needs (multimorbidity) rather than to delayed discharge. In other words, 'homeless service users' stay three times as long as they are [three] times as sick' ([name] and Halligan, 2010, p306). Despite this, there is strong evidence that a key problem facing homeless people in hospital is 'poor care' which often leads to difficulties accessing appropriate treatment, early 'self-discharge' and being discharged prior to being 'medically fit'. A review of hospital admission and discharge arrangements by Homeless Link (2012) identified 'countless examples' of the mention of homelessness on admission triggering prejudice among hospital staff. According to one homeless interviewee, 'As soon as [the nursing staff] find out you're homeless they want you out of the door' (p7). The review reported that more than 70% of homeless people were 'discharged straight back onto the streets, further damaging their health and all but guaranteeing their readmission' (p6). The main recommendation of the Homeless Link report is for cultural change in the way homeless people are viewed and treated in the NHS.

Other themes highlighted in the Homeless Link review and the literature more broadly include: hospital staff not asking people about their housing situation on admission and not addressing needs relating to drug and alcohol use (e.g. ensuring access to methadone); hospital staff not alerting accommodation providers to the fact that a person is in hospital leading to tenancies being terminated; hospital staff having a poor understanding of the services available to homeless people, including overestimating the level of care that can be provided in hostel settings leading to unsafe discharges; a lack of practical support, such as no replacement of soiled clothing; uncertainty regarding where the involvement of one sector should start and end, including little agreement about how far hospital staff should be expected to proactively seek accommodation; a lack of appropriate accommodation options raising the question of whether 'signposting' is an adequate response if this potentially leads to discharge back onto the streets

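### Admission group 4 is defined by support that comes after admission, so duration of stay is biased towards longer stay with SIHHC and admission-clock mortality carries immortal time

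*Protocol*

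**What the plan says.** Protocol, Stage 3b, Comparative Effectiveness Analysis, Study design, sorts admissions from November 2008 to November 2016 into five groups. It states that "through knowledge of the dates of SIHCC involvement and service user group we will be able to classify hospital admissions". Groups 1 and 2 are admissions in a deprived non-homeless population and in the Find and Treat homeless population. The other three concern the schemes' own service users:

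- Group 3: "Admissions in homeless service users prior to their first engagement with SIHCC".
- Group 4: "Admissions in homeless service users where there is evidence of SIHCC support for that admission".
- Group 5: "Admissions in homeless service users that occur following SIHCC support but where there is no record of support for the subsequent admission".

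The groups are compared by Cox models and Kaplan-Meier plots. The primary outcomes are time from discharge to next A&E attendance, 28-day emergency readmission, and "Time from discharge to next hospital inpatient readmission". The secondary outcomes include "Duration of inpatient admission", "Time from admission to death", time from admission to amenable death, and in-patient costs.

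The paragraph on confounding variables adjusts for age, gender, comorbidities and reason for admission by HRG. Neither length of stay nor method of discharge is listed, although Appendix One, Box 5 requests method of discharge from HES. The section gives no landmark, minimum stay or time-dependent exposure.

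**The concern.** Whether an admission counts as supported is known only after it has begun. If the team first meets the patient on the ward, a patient who leaves quickly cannot enter group 4, whatever scheme the hospital runs. The background makes such departures plausible: it names "early 'self-discharge' and being discharged prior to being 'medically fit" among the difficulties of this population, and says link workers assess in hospital only when they can.

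Two kinds of outcome are directly affected. Duration of stay is compared between a group selected for staying long enough to be met and groups without that selection. In-patient cost inherits the bias so far as it depends on stay, and the economic section says costs will include length of stay. For death timed from admission, the interval before first contact is survival that group 4 must have had; deaths in that interval fall elsewhere.

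This matters because the background reports a randomised trial of Pathway that found no change in length of stay and eased concern about delayed discharge. The planned comparison could show longer stay for a scheme with no effect on it.

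**Working it through.** **Plan's own figure.** The protocol gives none for this bias. The nearest benchmark is its sample size: (0.84 + 1.96)² × (0.7 + 0.6) / (0.7 − 0.6)² = 7.84 × 1.3 / 0.01 = 1019 person-years per group, as printed. The rate ratio it targets is 0.6/0.7 = 0.857; the stated 10% reduction would be 0.90. Neither tests the grouping, but they scale the readmission results below.

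**Inputs.** All are assumptions, because the protocol states no stay distribution and no contact delay.

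- Stay L: lognormal, log-SD 1, median 2, 3 or 5 days.
- Delay to first contact C: exponential with mean 1 or 3 days, or uniform over 0 to 7 days, independent of L.
- No effect of SIHHC on anything.

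**Rule.** An admission is supported if C < L and missed otherwise. Two ratios follow: E(L | C < L) / E(L | C ≥ L) against missed stays, and E(L | C < L) / E(L) against unselected stays.

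**Central case** (median 3, mean delay 3), by simulation. The unselected mean is 3 × e^0.5 = 4.95 days. About 62% of stays are supported. Mean stay is 6.7 days supported and 2.0 days missed; check: 0.62 × 6.7 + 0.38 × 2.0 = 4.9. The ratios are 6.73/2.03 = 3.3 and 6.73/4.95 = 1.36.

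**Full grid**, null ratio of mean stay (against missed / against unselected):

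| Median stay | Delay mean 1 d | Delay mean 3 d | Delay uniform 0–7 d |
|---|---|---|---|
| 2 d | 4.1 / 1.19 | 3.1 / 1.49 | 3.5 / 1.78 |
| 3 d | 4.8 / 1.12 | 3.3 / 1.36 | 3.9 / 1.57 |
| 5 d | 6.1 / 1.06 | 3.8 / 1.23 | 4.5 / 1.35 |

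A separate set of runs (median stay 3 days, exponential delays of mean 1 to 7 days, 5 to 20% self-discharge cutting stays short) gives 2.9 to 5.5 and 1.14 to 1.75.

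**Which ratio applies.** The unselected ratio suits groups 1 and 2, and much of group 3, which reaches back to November 2008 while scheme data start in November 2013. The missed-stay ratio suits the part of group 5 where the scheme did not reach the patient in time, and group 3 stays missed before a later engagement.

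**If post-discharge support counts.** Suppose half the missed stays in the central case are supported after discharge. The ratios fall to 2.8 against unsupported stays and 1.14 against all stays.

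**Readmission under no effect.** Assume self-discharge in 30% of stays under 2 days and 8% of longer ones, with 28-day readmission of 35% after self-discharge and 20% otherwise. Supported stays then show 21 to 23% readmission and missed stays 23 to 24%. In the separate runs (base rate 0.7 per person-year), the rate ratio against missed stays is 1.00 if self-discharge does not raise readmission, and 0.83 to 0.98 if it multiplies the rate by 1.5 to 2. If readmission also rises modestly with intended stay, as (stay/3)^0.1 to (stay/3)^0.2, the ratio is 1.02 to 1.25. The sign therefore depends on inputs the protocol does not give, and the size can approach the target of 0.857 or lie on the other side of 1.

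**Candidate fixes under the null.** Keeping only stays of at least 2 nights, with the group rule unchanged, leaves supported stays 1.9 to 3.5 times as long as unsupported ones. Keeping only stays that reach a landmark (day 1, 2 or 3) and classifying by contact before it gives a stay ratio of 0.99 to 1.00 and a readmission rate ratio of 1.00.

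The size of the immortal-time effect on mortality was not calculated; it needs early in-hospital death rates that the protocol does not give.

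**The case against.** Several objections narrow the point.

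- **Readmission.** A reader might infer that the grouping makes SIHHC appear to cut readmission. The document does not support that. All three primary outcomes are post-discharge outcomes, so no immortal time enters them. The background attributes long stays in this population to greater sickness, which pushes the other way.
- **Where missed stays go.** A reader might infer that every patient who leaves unseen lands in group 5. Group 5 requires earlier support. Someone engaged later goes to group 3; someone never engaged is in none of groups 3 to 5, and in group 2 only through Find and Treat. Nor does self-discharge vanish from group 4: under the 30% and 8% assumption, 9 to 17% of supported stays still end that way.
- **Meaning of support.** The text says support for the admission, not during it. Follow-on support might qualify, which weakens the selection. Pathway's weekly ward round is paper based and listed apart from nurse-led assessment, so it is not evidence of a seven-day wait.
- **Weight.** The person-level Poisson analysis and the sample size do not use groups 3 to 5, the admission-level models are described as exploring differences, and HRG adjustment may absorb some of the stay difference.
- **SAP.** A landmark or time-dependent exposure could appear in an SAP that is not shown.

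All but the last stand as limits. On the last, the group definition is fixed in the protocol, so an SAP that follows it inherits the problem. None of these removes the selection of group 4 on a post-admission event.

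**Conclusion.** The point holds for the secondary outcomes timed from admission. Where support begins in hospital, group 4 shows longer stay than its comparators under no effect, and deaths timed from admission carry immortal time. The stay ratio is about 1.1 to 1.8 against unselected admissions and 3.1 to 6.1 against missed stays, under the assumed stays and delays. The direction was the same in every scenario tested; the size rests wholly on assumptions and shrinks if post-discharge support counts. Unselected here means unselected on contact only, since groups 1 and 2 may differ from group 4 in other ways. For readmission and A&E attendance the supportable statement is weaker: selection on stay and self-discharge may distort them, in a direction the protocol does not settle.

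**What to change.** For duration of stay and for mortality timed from admission, use one of two approaches:

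1. Treat SIHHC support as time-dependent: the admission enters the supported state at its first involvement date and is compared with admissions still in hospital on the same day of stay.
2. Set a common landmark day, keep only stays in any group that reach it, and classify exposure by contact before it.

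A minimum stay without reclassifying exposure should not be used as the remedy. State whether support first given after discharge counts as support for the admission.

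For post-discharge outcomes, use the same landmark classification. Add a sensitivity analysis that defines exposure by whether a scheme was active at the admitting hospital on the admission date, whether or not support was recorded.

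The cost is mainly re-analysis, with real limits. Stays shorter than the landmark leave the contrast, and support first given after the landmark counts as unsupported. The analysis is confined to sites with usable involvement dates: the study design section assumes these are known, but Box 5 lists no explicit first-contact field, and contact dates are named only for the 378 consented users. The sensitivity analysis also needs each scheme's operating dates and the admitting hospital. Box 3 lists hospital of admission among transferred items, but the HES fields in Box 5 do not, so the data request should be checked.
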